### **Substance Use and HIV Risk among YMSM**

MSM use substances at higher rates than the general population, increasing HIV risk. High rates of drug and alcohol use among MSM relative to the general population have been documented, and our research has identified higher rates of drug use among YMSM compared to their heterosexual peers. Higher rates of drug use have also been documented among MSM, including YMSM in tandem with sexual activity. However, drug-use patterns seem to differ among YMSM with increased rates of cocaine use among YMSM, which could have implications for HIV risk given that stimulant use has been linked to condomless anal sex (CAS) and higher risk of HIV infection and other STIs. Nearly half of Black MSM with newly diagnosed HIV infection (48%) reported substance use during their last anal sex encounter. Substance use has been found to increase sexual risk behavior among MSM, placing them at high risk for CAS and HIV seroconversion, exchange sex, and greater number of sexual partners. Our own research using event level data for the previous 30 days has shown that substance use strongly and significantly predicts the odds of whether YMSM will use a condom. A number of other studies have looked

**PROTOCOL TITLE:** Comparative effectiveness trial of clinic-based delivery of an HIV risk reduction intervention (YMHP) for YMSM, Phase 2

at the impact of substance use on sexual behavior and increased odds of seroconversion. Different substances are associated with sexual risk behavior among specific groups. Among Latino MSM, methamphetamine use and among Black MSM higher rates of marijuana use have been linked to sexual risk. Therefore, there is a critical need for brief, culturally appropriate, effective behavioral interventions that improve self-management to reduce new HIV infections among substance using YMSM.

**Effectiveness of Motivational Interviewing**

Motivational interviewing (MI) has the potential to improve self-management behaviors in terms of promoting sexual health and reducing substance use among YMSM. There is strong evidence that MI is a culturally appropriate and effective approach for working with racial and ethnic minority populations who are disproportionately affected by HIV. One meta-analysis of MI found greater effect among minorities. MI has been recommended as particularly effective when working with YMSM. MI promotes increased intrinsic motivation to change and, when paired with information regarding health risk behaviors, reinforces the individuals' right and capacity to make well-informed health self-management decisions for themselves. YMHP was the first trial of a structured and manualized MI intervention that also included personalized feedback and problem-solving skills building to reduce CAS and substance use in YMSM. As such, YMHP has the potential to have a significant impact on YMSM seeking sexual health or HIV counseling and testing (HIV C&T) services at clinics.

**Remote Delivery**

Research on telephone-based MI (TBMI) has consistently found that it produces significant improvements in a wide range of physical health challenges. Furthermore, TBMI reduces mental health and alcohol related problems as well as sexual risk-taking among people living with HIV. Research comparing the effects of TBMI to face-to-face (clinic-delivered) interventions has produced equivocal results. Across studies examining physical activity, mental health, and substance use outcomes, findings suggest no significant differences in delivery method. Carey et al. examined relative efficacy of a telephone versus face-to-face intervention for alcohol use and observed a significant interaction of delivery method with gender. Women on average had better outcome in the face-to-face condition, while men responded equally well to both delivery methods.

Notably, the issue of health care access has not yet been examined as a moderator of relative effectiveness. One advantage of TBMI is that it significantly reduces patient burden. It is therefore plausible that it will show superior effects among YMSM who experience barriers to health care access. However, it is also possible that remote delivery (via phone or video chat using Skype/FaceTime) will decrease engagement and the quality of the relationship between the community health worker (CHW) and the participant. This may result in clinic-based delivery being superior among YMSM who have better access to healthcare. Understanding how health care access intersects with delivery method will substantially inform implementation decisions at clinics and other agencies seeking to utilize YMHP.

We are proposing to give participant the choice of conducting the YMHP Session in person at the clinic or remotely. We find that giving participants the option of delivery modality has the

PROTOCOL TITLE: Comparative effectiveness trial of clinic-based delivery of an HIV risk reduction intervention (YMHP) for YMSM, Phase 2

potential for increasing session retention over randomizing participants to receive either at the clinic or remote delivery. Our new study design will be able to examine those differences.

COVID accommodations- We are also giving the option of completing the YMHP intervention in the clinic, but virtually. This means that the participant would come to the clinic for the appointment, but virtually meet with the CHW in a different room. The procedures would be similar to remote delivery. This reduces the amount of time a participant and a CHW are in the same room together.

### **CHW Intervention Delivery**

Integrating Implementation Science into a comparative effectiveness trial (CET) can minimize the science-practice gap. MI providers need not be clinicians – one study conducted by our team comparing CHWs to clinicians found both were equally effective in providing high quality MI and that clients were more likely to be retained in HIV care when working with CHWs. CHWs are commonly integrated into clinics, and often play a central role in providing HIV prevention services, including HIV C&T. Training CHWs to deliver evidence-based interventions is a critical step towards realistic and cost-effective implementation. The Centers for Disease Control and Prevention (CDC) has called for expanded use of CHWs in the prevention and management of chronic diseases with attention to implementation and training.

Several steps will be taken in this CET to promote adoption and sustainability of the YMHP intervention. First, using staff embedded in the clinic can build capacity for implementation. Second, CHWs have long been the cornerstone of integrating support services into HIV-related prevention efforts. Training CHWs to deliver interventions is a critical step towards realistic and cost-effective implementation. Research has documented the amount of training needed to obtain MI fidelity, concluding that initial training followed by ongoing coaching is required. Such training can be costly when relying on outside trainers. Thus, a “train the trainer” model, where expert trainers provide local supervisors with MI coaching skills, may be more sustainable.

## **4.0 Study Endpoints**

The primary goals of the study are to compare how clinic-based or remote delivery of YMHP help improve sexual health management (as measured by decreased STIs, CAS, and increased PrEP uptake/adherence) as well as reduce substance use among YMSM over a standard of care HIV testing and counseling.

## **5.0 Study Intervention**

### **Intervention Design and Procedures**

YMHP is a CDC Best Evidence Intervention that utilizes motivational interviewing (MI) to reduce CAS and substance use among YMSM. The YMHP intervention will be delivered by MI-trained CHWs employed at clinics, primarily by former HIV C&T counselors, health educators, and trained program peers. Participants will be randomized to receive the intervention either in person or remotely. Both conditions involve completion of the 4 YMHP sessions and the delivery of PrEP information and navigation services to interested participants.

YMHP is a CDC Best Evidence Intervention that utilizes motivational interviewing (MI) to

**PROTOCOL TITLE:** Comparative effectiveness trial of clinic-based delivery of an HIV risk reduction intervention (YMHP) for YMSM, Phase 2

reduce CAS and substance use among YMSM. The YMHP intervention will be delivered by MI-trained CHWs employed at clinics, primarily by former HIV C&T counselors, health educators, and trained program peers. Participants will be randomized to receive the intervention either in person or remotely. Both conditions involve completion of the 4 YMHP sessions and the delivery of PrEP information and navigation services to interested participants.

**Intervention Training and Supervision**

YMHP training will occur prior to the initiation of Phase 2, with ongoing coaching and supervision and training of new interventionists, as required. The interventionist training team consists of members of PRIDE Health Research Consortium's clinical team and include at least one member of MINT. The YMHP training procedure includes:

1. Initial three-day training for CHWs and local supervisors;
2. A two to three-month training period of role-play practice, coding and feedback, and supervision modeling, including mock sessions with "standardized clients" role played by Research Assistants;
3. One hour weekly supervision sessions between local supervisors and CHWs;
4. Monthly supervision calls between local supervisors and the investigator team, including a quarterly Skype booster training; and
5. Ongoing quality assurance and feedback using MITI coding.

All materials (e.g., slides, training exercises, supervisory tools) will be packaged for potential dissemination. Prior to dissemination, any copyrighted media will be removed from these materials. The three-day training will be held in Miami and follows a curriculum developed for our previous National Institutes of Health-funded effectiveness trials. CHWs and supervisors participate together in days 1 and 2 of the training. The third day of training will be split so that CHWs can have more practice with the YMHP protocol, and supervisors can focus on coaching MI. REC will provide external MITI coding for the supervisor to use as feedback. Following the 3-day training workshop, all CHWs and supervisors will submit audio recordings of all intervention sessions completed with a mock client. These sessions will be MITI coded and REC trainers will provide coaching and feedback. Once beginner competency is met, the local clinic supervisor will take over weekly individual supervision of the CHWs. If there is staff turnover for any reason (e.g., staff leave the clinic, staff are unable to be cleared to see participants due to quality of delivery), then additional training will be provided to new staff members.

The PRIDE Health Research Consortium Clinical Team will lead quarterly boosters via group Skype for supervisors. Prior to the quarterly boosters, supervisors will submit a recording of a supervision session for review. Boosters will cover successes and challenges, MITI scores, updated MI skill development plans for each CHW, and role-plays of supervision skills.

Someone from the Clinical Team will join supervision sessions via Skype if MITI scores fall below competency without remediation. They will also lead annual in-person booster trainings covering MI skills and specific delivery of YMHP for supervisors and CHWs.

**Assurance of Intervention Fidelity**

All sessions (remote and clinic-based) will be audio-recorded and sent for MITI coding. For the pre-trial phase, both CHWs and supervisors will mock the intervention and submit 4 roleplays of

**PROTOCOL TITLE:** Comparative effectiveness trial of clinic-based delivery of an HIV risk reduction intervention (YMHP) for YMSM, Phase 2

intervention in-person and 4 roleplays of the intervention remotely delivered. Then supervisors will complete one session of supervision with each CHW and audio recordings will be uploaded onto the site Dropbox Business account.

Mocks will be coded using MITI thresholds for fidelity flagging. Those 5 criteria are: percent reflection, percent complex reflection, technical global, relational global and MI non-adherent (MINA) codes. For clearance, trainees should be scoring in the “fair range” on all 5 elements by their final mock. If they are below in one or two areas, they don’t have to redo the mock. However, by the mock of Session 4 they should be at least “fair” in all elements to be cleared.

For ongoing monitoring, MITI coding randomizer should flag for additional review any session where the CHW falls below fair on more than 2 of those domains. One recording per CHW will be randomly selected for MITI coding by the study team on a regular basis. All the randomly coded sessions, not just the flagged MITI forms, will be shared with the supervisors for them to trust their barometers for “good enough” MI instead of only having MITI to compare when things were “bad.”

For the full-trial, each CHW will complete and submit an electronic Clinical Session Form via Qualtrics upon completion of each YMHP session.

## **6.0 Procedures Involved**

### **Enrollment and Consent**

Utilizing enrollment procedures established within ATN, SRV staff will invite YMSM who are identified through outreach, at their clinic, or through mobile testing efforts to screen for the study. Those interested will complete a brief iPad eligibility screener. HIV testing may be conducted after the screener and before the baseline appointment. If eligible on the screener, SRV study staff will schedule the potential participant for a baseline assessment. Potential participants will complete informed consent following ATN-wide established protocols. This will occur at the beginning of the baseline visit, prior to assessment, but after any HIV testing.

After a potentially eligible participant has given their informed consent to participate in the study, they are then asked to complete the baseline CASI and complete STI testing. Participants are deemed eligible for the study based on screening data and no longer need verification at baseline appointment.

Participants who were enrolled prior to November 1, 2019 will be given a consent/assent addendum at their next follow-up appointment which introduces the long-chain referral and qualitative interview options. Since their initial consent form did not include these items, the addendum will give them the option to receive incentives for providing referrals to the study and to participate in the optional qualitative interview.

### **Randomization**

Participants will be randomized after completing the baseline assessment (i.e., CASI and specimen collection), but prior to their first YMHP session. Participants are randomized into one of two intervention conditions: 1) YMHP (delivery of the YMHP intervention in person or

**PROTOCOL TITLE:** Comparative effectiveness trial of clinic-based delivery of an HIV risk reduction intervention (YMHP) for YMSM, Phase 2

remotely), or 2) a standard of care HIV Testing and counseling session with referrals to other available services. . If the participant is randomized to YMHP, the first YMHP session will always be conducted in person after the baseline assessment. In the event a participant does not wish to complete the first YMHP session immediately after the baseline assessment, the SRV will postpone the participant's randomization. Randomization will then occur when the participant returns to the SRV for their first YMHP session. If the participant is randomized to HIV Testing, no additional intervention procedures are required, because HIV testing is conducted in conjunction with the Baseline appointment. However, the CHW will meet with the participant to ensure that any individual risk assessment is administered and referrals for PREP and other prevention services are given consistent with clinic standards of care for individual HIV testing.

**COVID accommodations-** In the event the baseline visit is conducted virtually (see below for details), randomization will still occur after HIV Testing and before the intervention. Since many individuals who are randomized to HIV testing only will have already received that portion of the appointment, randomization may occur before scheduling session 1.

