Intervention sessions should occur approximately once per week for 4 weeks with the first session immediately after completion of the baseline assessment. Participants will complete three additional YMHP sessions focused on sexual risk and substance use. The sessions will be completed at the SRV or remotely depending on randomization. All sessions will be audio recorded and should take approximately 40-60 minutes to complete. No video will be recorded. There is a 12 week window for intervention sessions completion, i.e. all four sessions should be completed within 12 weeks of the baseline assessment. Thus, if participants need to miss a week periodically, for any reason, they should have ample time to complete the four sessions during the 12-week window. The participant will make arrangements to have the session be delivered at the clinic or remotely. Each session can be different depending on what works best for the participant.

*YMHP sessions:*

2nd session: \$10

3rd session: \$10

4th session: \$10

Bonus (if attend all sessions): \$20

Audio-recording the intervention sessions is part of the consent/assent process for participation

**PROTOCOL TITLE:** Comparative effectiveness trial of clinic-based delivery of an HIV risk reduction intervention (YMHP) for YMSM, Phase 2

into YMHP. During the intervention session, the participant can be reminded that the sessions are confidential and recorded only for quality assurance purposes. If the participant declines to be audio recorded, then they cannot participate in the session, but can remain in the study and complete the follow-up assessments.

Due to COVID- All YMHP sessions (including Session 1) can be delivered in person or remotely.

*B. (HIV testing condition)*

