HIV testing is a prevention service already provided by the staff at each SRV as part of their existing outreach and testing services (which are funded and monitored by local health department and CDC contracts). Everyone who is enrolled into the study will have had HIV testing as part of the screening process prior to study enrollment. If a participant is randomized to standard of care HIV testing, they will not attend any further sessions. The study staff will ensure that the participant has received referrals to available services, including PrEP services. They will be scheduled for their immediate post-test assessment 3 months after BL. They will also be given the option to complete the 4 YMHP Sessions after the 9month follow-up (12month follow-up post BL).

*Immediate Post-test Assessment (3 months after BL)*

After completing YMHP sessions, participants will be scheduled to complete an immediate post-test assessment (IP). This assessment will occur about three months after their baseline assessment (i.e., the first follow-up assessment post-baseline). During this assessment participants will complete a CASI about their drug use, sexual behavior and general thoughts and feelings. In addition to assessing the primary outcomes of the intervention, participants will also respond to process measures. Specifically, participants will be asked to provide an evaluation of their counselor, as well as the health care climate of the YMHP intervention. This CASI can be completed at the SRV or remotely. Participants access the CASI through a survey link sent directly to their email, and takes approximately 45 minutes to complete.

During this visit (or anytime after the Intervention window closes, which is 3 months after Baseline) a participant may be asked to participate in an optional qualitative feedback interview. Participants will be called by a research staff member at PRIDE or at one of the other sites to complete a 30 minute interview over the phone. This interview will be offered in the immediate post test assessment, but can be completed at any time 3 month after the BL.

*Immediate post-test assessment*

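### Randomisation can be postponed with no stated limit while the session window and visit schedule run from baseline, so late-randomised participants have less time between allocation and each assessment

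*Protocol*

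**What the plan says.** Protocol 6.0, Randomization, places allocation after the baseline survey and specimens and before the first YMHP session. If the participant does not want that session at once, "the SRV will postpone the participant's randomization", and "Randomization will then occur when the participant returns to the SRV for their first YMHP session". No longest permitted interval is stated. Section 14.0 recognises the gap (a participant who withdraws in it is not randomised), but sets no limit and describes no repeat baseline.

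The rest of the schedule is counted from baseline:

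- Sessions: "Intervention sessions should occur approximately once per week for 4 weeks with the first session immediately after completion of the baseline assessment", with an outer limit that "all four sessions should be completed within 12 weeks of the baseline assessment".
- Immediate post-test, YMHP arm: it is to follow completion of the sessions, and also "This assessment will occur about three months after their baseline assessment".
- Immediate post-test, HIV-testing arm: "They will be scheduled for their immediate post-test assessment 3 months after BL".
- Later visits: 3, 6 and 9 months after the post-test, so about 6, 9 and 12 months after baseline.

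The SAP (1.2) fits growth models with an intercept and a linear slope and interprets a post-intervention intercept. It names no time origin and does not mention the interval between baseline and randomisation.

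**The concern.** The treatment comparison starts at randomisation, but the visit schedule starts at baseline. For anyone whose allocation is postponed, every week of delay is taken from the time available to deliver YMHP and to observe its effect. The post-test must come after the sessions and also about three months after baseline. For a late enough return both cannot hold, and no rule says which prevails.

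Three things are at stake. First, the post-test effect is averaged over participants with very different times since allocation, which dilutes it and blurs the intercept that the SAP wants to interpret. Second, sessions may be lost to a window that was running before the participant was allocated. Third, the baseline ages. An HIV-negative test that is 80 days old at baseline, allowed under the 90-day criterion in 10.0, is 80 + 28 = 108 days old after a four-week postponement. PrEP started between baseline and randomisation would look like uptake after baseline although it preceded allocation.

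**Working it through.** **Inputs.** Four sessions about a week apart; session window 12 weeks (84 days) from baseline; post-test at 3 months, 365.25/4 = 91.3 days, about week 13; last visit 9 months after the post-test, about week 52 (all from Protocol 6.0). Let randomisation and session 1 fall d weeks after baseline. Exact weekly spacing is my assumption; the protocol says approximately weekly.

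**The plan's own schedule (d = 0).** Session 4 falls at week 3. That leaves 12 − 3 = 9 weeks of slack in the window and 13 − 3 = 10 weeks before the post-test.

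**Formulas.** Session 4 at d + 3. A full course fits if d + 3 ≤ 12, so d ≤ 9. Session 4 to post-test: 13 − (d + 3) = 10 − d. Randomisation to post-test: 13 − d. Randomisation to last visit: 52 − d.

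| d (weeks) | Sessions inside window | Session 4 to post-test | Randomisation to post-test | Randomisation to last visit |
|---|---|---|---|---|
| 0 | 4 | 10 | 13 | 52 |
| 4 | 4 | 6 | 9 | 48 |
| 8 | 4 | 2 | 5 | 44 |
| 9 | 4 | 1 | 4 | 43 |
| 10 | 3 | 0 | 3 | 42 |
| 11 | 2 | −1 | 2 | 41 |
| 12 | 1 | −2 | 1 | 40 |
| 13 | 0 | −3 | 0 | 39 |

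From d = 10 the third column supposes that sessions run past the window. A negative entry means that the post-test comes before session 4.

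**Reading the table.** Up to week 9 the whole course precedes the post-test and only the interval shrinks. From week 10 there are two possibilities. If the window is kept, 3, 2 or 1 sessions fit at weeks 10, 11 and 12. If sessions run past it, session 4 coincides with the post-test at week 10, the post-test falls within the course at weeks 11 and 12, and from about week 13 it falls at or before session 1. The documents do not say which applies.

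**Where it bites.** At d = 9 the post-test keeps 4/13 = 31% of its planned time since randomisation, while the last visit keeps 43/52 = 83%. At d = 12 the figures are 1/13 = 8% and 40/52 = 77%. The loss is concentrated at the post-test.

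**Possible dilution (illustration only).** The documents give no share postponed. Suppose a share q shows no effect at the post-test because of a late start, and that the analysis would otherwise have a nominal 80% power at two-sided 5%. Power is then Φ[(1.960 + 0.842)(1 − q) − 1.960]:

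- q = 5%: 76%
- q = 10%: 71%
- q = 20%: 61%
- q = 30%: 50%

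No effect at all is the harsh case. Participants who start late but finish their sessions would lose less.

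**The case against.** A reader might infer that late-randomised participants are in general assessed during or before YMHP. The text does not support that. The sessions are meant to end within 12 weeks of baseline, and the post-test comes after both the sessions and that window: the qualitative interview, for instance, may be held at that visit or "anytime after the Intervention window closes, which is 3 months after Baseline". Assessment during or before YMHP needs a delay of about ten weeks or more and, in addition, sessions run past the stated window.

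A reader might also infer bias between arms. That does not follow either. Postponement happens before allocation and the post-test is timed from baseline in both arms, so the gap has the same expected distribution in each. The comparison remains a valid randomised one, over a mixture of exposure times.

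Other points stand:

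- The post-test is survey-only. STI, HIV and urine drug tests come at the visits 3 and 9 months after it, well after the sessions for anyone who finishes within the window.
- Overlap between recall and sessions is not special to postponement. If the survey used the 30-day period in the SAP's power section (its actual recall period is not stated), overlap with session 4 would begin once 7(d + 3) exceeds 91 − 30 = 61 days, at about d = 6. A participant randomised on the baseline day who misses weeks and finishes at week 12 has the same overlap.
- That youth with barriers to care postpone more is plausible but unsupported. The stated trigger is not wanting session 1 at once, after a visit that may last 3 to 4 hours.
- Randomising at session 1 has a real advantage: it limits loss between allocation and first receipt of YMHP.
- Section 6.0 (Enrollment and Consent) says that eligibility rests on screening data and needs no verification at baseline, so not re-reading the criteria is a choice for everyone.
- For virtual baselines the COVID text lets randomisation precede the scheduling of session 1, so the return-visit rule does not govern every route.

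None of this supplies a maximum gap, a rule for late returns, or a reason to run the visit schedule from baseline rather than from allocation.

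**Conclusion.** The concern holds in a limited form. The rules as written shorten the time from randomisation to post-test one week for each week of postponement, without a stated bound, and four weekly sessions cease to fit the window after about week 9. The result is some dilution of the YMHP effect, uneven follow-up time and an older baseline, mainly at the immediate post-test. It is not bias between arms. The schedule arithmetic rests only on the stated timings and weekly spacing. The overall effect on the trial depends on how many participants postpone and for how long, which the documents do not report; it could be negligible. This is an inexpensive improvement to a stated rule, not a flaw that undermines the comparison.

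**What to change.** 1. Time the immediate post-test from the date of randomisation in both arms. The later visits follow through it. Randomisation to post-test is then about 13 weeks whatever d is.
2. In the SAP, name randomisation as the time origin of the growth models.
3. Reconcile the session-window wording in 6.0 (Randomization, the YMHP sessions text and the post-test text) so that it says what applies to a late-randomised participant. The choice of rule is the sponsor's.
4. State a maximum interval from baseline to randomisation, of the sponsor's choosing, beyond which the baseline survey is repeated before allocation. A repeat survey cannot refresh the HIV-negative test, a positive STI result or the specimens, so state separately how those are handled.
5. Report the distribution of the interval from baseline to randomisation.

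The cost is protocol and SAP wording, a scheduler change, a repeat survey for those beyond the limit, and calendar follow-up that is d weeks longer for a participant postponed by d weeks. Nothing changes for those randomised on the baseline day.
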